5.4 SUBJECT WITHDRAWAL/DISCONTINUATION

5.4.1 REASONS FOR WITHDRAWAL/DISCONTINUATION

A subject will be withdrawn from the study for the following medical or administrative reasons:

- Occurrence of an AE that represents an unacceptable risk to the subject and when continued

participation in the investigational study is not warranted, in the judgment of the investigator, Sponsor, or medical monitor. The investigator must follow the subject until the AE resolves or is stable, unless the subject is lost to follow up.

- Treatment with a prohibited concomitant medication other than the use of appropriate medications for the treatment of AEs under direction of the investigator.
- Subject noncompliance, defined as refusal or inability to adhere to the trial schedule or procedures.
- At the request of the subject or the subject's LAR (e.g., subject withdraws consent), investigator, Sponsor, or regulatory authority.
- Pregnancy.
- A subject will be discontinued if the number of IDH events during a treatment period exceeds a predetermined threshold above the subject's Historical IDH Rate after de-escalation to the lowest column size (see [Appendix 17.1](#)).
- A subject will be discontinued if Hgb levels remain < 9 g/dL despite optimized iron and ESA treatment and after de-escalation to the lowest column size (see [Appendix 17.1](#)).

In the event of early withdrawal/discontinuation of a subject who has been randomized and received at least 1 HD treatment, the EOS procedures will be performed unless the subject has withdrawn consent.

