6.1.5 COLUMN SIZE ESCALATION AND ADMINISTRATION

The initial AKST1210 size used during Weeks 1 to 4 (Treatment Period 1) will be the 150 mL column

(AKST1210 S-15). Following evaluation for IDH Rate and anemia (see [Appendix 17.1](#)), subjects may be escalated to the 250 mL column (AKST1210 S-25) for Weeks 5 to 8, followed by the 350 mL column (AKST1210 S-35) for Weeks 9 to 12. The subject, investigator, and outcomes assessor must remain blinded to treatment assignment at all times. Careful attention should be given to ensure that all subjects, regardless of treatment assignment, undergo the same evaluations for escalation, de-escalation, and discontinuation.

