17 APPENDICES

APPENDIX 17.1 ESCALATION, DE-ESCALATION, AND DISCONTINUATION RULES FOR TREATMENT WITH AKST1210 OR CONTROL

The following definitions are relevant to evaluating whether to escalate, de-escalate, or discontinue a subject:

- **Intradialytic hypotension/hypotensive event (IDH):** A decrease in SBP \geq 20 mm Hg or a decrease in MAP \geq 10 mm Hg associated with symptoms that include: abdominal discomfort; yawning; sighing; nausea; vomiting; muscle cramps; restlessness; dizziness or fainting; and anxiety ([K/DOQI Workgroup 2005](#)).
- **Expected IDH Rate:** The expected number of occurrences of IDH per 4-week treatment period used to assess escalation, de-escalation, and discontinuation. Expected IDH is derived from a subject's Historical IDH Rate (see table below).
- **Historical IDH Rate:** The number of occurrences of IDH as documented in a subject's medical record during a recent, consecutive 8-week interval prior to randomization. This 8-week period may include the 2-week Run-in. Subjects with 5 or more IDH events during this 8-week interval will be excluded.

The table below provides the corresponding Expected IDH Rate based on the Historical IDH Rate and summarizes the rules for escalation, de-escalation, or discontinuation based on the number of occurrences of IDH.

Historical IDH Rate over 8 weeks	Expected IDH Rate over 4 weeks	Escalation Rule	De-escalation or Discontinuation Rule
0	0	1 or less	2 in 4 weeks
1	1	2 or less	3 in 4 weeks
2	1		
3	2	3 or less	4 in 4 weeks
4	2		

Escalation Rules: A subject may be escalated to the next larger column size if they experience no more than 1 IDH event above their Expected IDH Rate in a 4-week treatment period and has an Hgb level \geq 9 g/dL.

De-escalation Rules: A subject should be de-escalated to a previously tolerated column size if at any time during a 4-week treatment period they experience 2 or more IDH events above the Expected IDH Rate and/or has a Hgb level $<$ 9 g/dL despite optimized ESA treatment.

Discontinuation Rules: A subject should be discontinued if they experience 2 or more IDH events above their Expected IDH Rate in a 4-week treatment period after de-escalation to the lowest column size (AKST1210 S-15) and/or has an Hgb level $<$ 9 g/dL despite optimized ESA treatment after de-escalation to the lowest column size (AKST1210 S-15). Subjects may also be discontinued at any time at the discretion of the investigator.

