	
Added:
 
 • The change in IDH Rate above each subject's Historical IDH Rate for each column size. • The incidence of IDH leading to de-escalation or discontinuation. • The incidence of worsening anemia by column size. • The incidence of anemia leading to de-escalation or discontinuation. 
Previously read: Change from baseline in b2M concentration in post-HD circuit and post-AKST1210 levels by column size and duration of treatment at Week 4, Week 8, and Week 12, and Week 14 at End of Study (EOS) (2 weeks after treatment conclusion).
 
Now reads: Change from baseline in levels of b2M at Weeks 4, 8, 12 and EOS and evaluation of any differences in the magnitude of change based on column size and duration of treatment with a specific column size.
 
Previously read: Change in cognition per the Cogstate test battery (i.e., verbal learning, psychomotor function, visual attention, working memory, executive function, and verbal delayed recall).
 
Now reads: Change in cognitive domains as measured with the Cogstate battery (i.e., verbal learning, psychomotor function, visual attention, working memory, executive function, and verbal delayed recall).
	Revised for clarity and to enable quantification of the occurrence of IDH and anemia.
Protocol Summary (Subject Duration), Schematic of Study Design	Screening period extended from -4 to -2 weeks to -6 to -2 weeks (-42 to -14 days); thus, duration for subjects may be extended an additional 2 weeks (also see changes to Schedule of Study Events [15.1.1] detailed below).	Screening period extended to enhance study feasibility.
2.3.1, Table 1	Modified Table 1 to provide more explicit mitigation strategies/preventative measures for IDH and anemia.	Updated to provide clarity regarding mitigation strategies that serve to minimize the risk of IDH and anemia from occurring in study subjects.
2.3.1	Added: [...] because data on the potential effects of	Updated to provide guidance

	AKST1210 on plasma levels of medications are limited, it is recommended that all IV and oral medications be given after each dialysis session, unless clinically needed before or during dialysis.	as to the timing of IV medications given that data regarding potential clearance of medications is limited.
4.1, Schedule of Events	Extended Screening Visit window from 2 weeks (Day -28 to -14) to 4 weeks (Day -42 to -14).	To enhance feasibility of performing required screening assessments within window.

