	
Added exclusion criterion #14 as follows: Subjects with a hemoglobin level < 9 g/dL.
 
Updated exclusion criterion #15 (previously #12) as follows: Previously read: Concurrent or recent participation in another investigational clinical trial.
 
 Prior clinical trial subjects must have discontinued investigational agents at least 30 days prior to Screening for small molecules, and 1 year prior to Screening for vaccine or immunotherapy agents. 
Now reads: Concurrent or recent participation in another investigational clinical trial. Prior clinical trial subjects must have discontinued investigational agents at least 30 days prior to Screening.
 
Updated exclusion criterion #16 (previously #13) as follows: Previously read: History of severe depression/suicidality requiring hospitalization.
 
Now reads: History of severe depression/suicidality requiring hospitalization in the last 6 months.
	
Incorporated to exclude subjects with anemia.
 
Clarification of timing of use for investigational agents prior to Screening.
 
Clarification of timing of hospitalization for severe depression/suicidality.

5.3, 5.4.2	Content revised to indicate that subjects who discontinue or are unblinded prior to Week 8 may be replaced (previously indicated prior to Week 5).	Revised to provide clarity regarding timing for replacement of subjects.
5.4.1	
Added:
 
 A subject will be discontinued if the number of IDH events during a treatment period exceeds a predetermined threshold above the subject's Historical IDH Rate after de-escalation to the lowest column size (see Appendix 17.1). A subject will be discontinued if hemoglobin levels remain < 9 g/dL despite optimized iron and ESA treatment and after de-escalation to the lowest column size (see Appendix 17.1). 	Clarification to align with revised Definitions, study procedures, and Appendix 17.1.
6.1.2.1	Clarified that the control will consist of a covered surrogate object of similar size/shape as the AKST1210 column and incorporated a reference to the Device Procedures Manual.	Revised for clarity and consistency.
6.1.5	Added: Careful attention should be given to ensure that all subjects, regardless of treatment assignment, undergo the same evaluations for escalation, de-escalation, and discontinuation.	Added for clarity and to ensure adequacy of blinding procedures.

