Appendix 17.1	Updated the escalation, de-escalation, and discontinuation rules to specify criteria related to the occurrence of worsening anemia. Under the revised criteria, subjects with a hemoglobin (HgB) < 9 g/dL will not be escalated to the next column size and subjects whose HgB decreases to < 9 g/dL at a given column size despite optimized ESA treatment will be de-escalated or discontinued as applicable.	Updated to account for monitoring of anemia and to provide enhanced clarity concerning escalation, de-escalation, and discontinuation rules.
Appendix 17.2	Appendix was eliminated.	Duplicative content was removed for clarity.

Protocol Version 1.2 dated 13NOV2019
Replaces: Protocol Version 1.0 dated 11OCT2019

The following table describes changes from Version 1.1 (dated 11OCT2019) with justifications provided.

Section(s)	Description	Justification
Throughout	Protocol version update. Previously read: V1.1_11OCT2019 Now reads: V1.2_13NOV2019	Version control.
Throughout	Minor grammar and content updates.	Minor grammar/content updates for clarity/accuracy of content.
Table of Contents	Minor content updates.	Minor updates required to reflect revised content.
List of Abbreviations	Minor content updates.	Minor updates required to reflect revised content.
6.1.2.1	Content revised to remove term “control device” and replace with “control” only.	Revised to prevent confusion regarding control.
6.2, 15.1.2, 15.1.3, 15.1.4, 15.1.5	Control accountability added to heading (6.2) and content of sections.	Revised to include accountability for control.
8	The following sentence was added, “When assessing relatedness, it should be assumed the subject was randomized to the AKST1210 column unless unblinding is required.”	Revisions related to prevention of inadvertent unblinding.
8.1.2	Section removed and Section 8.1.3 renumbered to Section 8.1.2.	Device deficiencies and user errors will now be reported as technical errors.
8.2.1	Term “ADE” added to section.	Provide clarity regarding adverse event classification.
8.2.3	Heading changed to, “Expectedness of Adverse Device Effects.”	Provide clarity regarding section content.
8.2.3.1	Second paragraph revised to information regarding assessment and reporting of a UADE.	Provide clarity regarding UADE assessment and reporting.
8.3.1	Heading changed to “Post-Study Safety Assessment.”	Avoid use of abbreviations in heading per style guidelines.

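### The Hgb < 9 g/dL discontinuation rule covers S-15 only after a step-down, so a subject below 9 g/dL on first-assigned S-15 meets no visible mandatory stop

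*Protocol*

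**What the plan says.** The Hgb discontinuation rule appears in two places. Appendix 17.1 applies it to a subject below 9 g/dL "despite optimized ESA treatment after de-escalation to the lowest column size (AKST1210 S-15"). Section 5.4.1 discontinues a subject whose "Hgb levels remain < 9 g/dL despite optimized iron and ESA treatment and after de-escalation to the lowest column size"; it adds iron to the treatment condition but keeps the step-down condition.

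Three other provisions bear on the case:

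- **Starting size.** Section 6.1.5: "The initial AKST1210 size used during Weeks 1 to 4 (Treatment Period 1) will be the 150 mL column". Table 2 in Section 6.1.2.1 shows that this S-15 model is the smallest of three, with 65 mL extracorporeal volume.
- **De-escalation.** Appendix 17.1: "A subject should be de-escalated to a previously tolerated column size", triggered by excess IDH events or by Hgb below 9 g/dL despite optimized ESA treatment.
- **Discretion.** Appendix 17.1: "Subjects may also be discontinued at any time at the discretion of the investigator".

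The revision log (Section 18.1) describes the Appendix 17.1 edit as meaning that subjects whose Hgb drops below 9 g/dL "at a given column size despite optimized ESA treatment will be de-escalated or discontinued as applicable". It also records an added exclusion criterion at the same limit: "Subjects with a hemoglobin level < 9 g/dL".

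**The concern.** The step-down precondition leaves out the column size on which every active subject begins. In Treatment Period 1, and later for anyone never escalated, S-15 is the assigned size and not the result of de-escalation. Read literally, the rule that protects a subject who stepped down to S-15 does not protect one who has never left it.

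Two things are at stake:

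- **Safety and consistency.** The subject stays on the column unless someone exercises judgment, and blinded investigators at up to 5 sites could act differently on the same Hgb value. Safety is the primary objective of this trial.
- **A secondary endpoint.** The incidence of anemia leading to de-escalation or discontinuation (Protocol 4.2.2, SAP 5.7.6) counts this subject only if someone chooses to stop treatment. A subject kept on S-15 adds nothing to it, although the worsening-anemia endpoint (SAP 5.7.5) may still capture the event.

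**Working it through.** **Step 1. Apply each visible rule to one state: on S-15 as first assigned, Hgb < 9 g/dL despite optimized ESA treatment.**

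| Rule | Result |
|---|---|
| Escalation (Appendix 17.1) | Barred, since it needs Hgb of at least 9 g/dL. The subject stays on S-15. |
| De-escalation (Appendix 17.1) | Trigger met, but the action is impossible: there is no earlier or smaller size. |
| Discontinuation (Appendix 17.1) | Precondition of prior de-escalation not met. |
| Discontinuation, Hgb item (Section 5.4.1) | Same precondition not met. |
| AE-based withdrawal (Section 5.4.1) | Rests on judged unacceptable risk; no Hgb threshold. |
| Investigator discretion (Appendix 17.1) | Permitted, not required. |
| Medical monitor and DSMB review (Section 8.6) | Judgment; no Hgb threshold. |

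No visible rule requires stopping or makes a size reduction possible.

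**Step 2. Change only the route to S-15.** Suppose the subject had gone to S-25 and come back. With the same Hgb, column and ESA status, both discontinuation texts now apply. The visible text gives no reason for the difference.

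**Step 3. Compare IDH.** The IDH discontinuation sentence in Appendix 17.1 has the same step-down wording. For IDH, however, Section 7.1.1.2.2 requires de-escalation or discontinuation as appropriate, and the Appendix 17.1 table has one joint column for both actions. Both concern IDH only, so IDH has just a wording inconsistency while Hgb has a gap.

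**Step 4. Upper bound on exposure.** Sections 15.1.2 to 15.1.5 schedule 12 sessions in each of three periods: 3 × 12 = 36, from Day 1 to Day 82. Section 15.2 checks Hgb on Days 1, 15, 29, 43, 57 and 71. Day 1 is the first session, so the count starts at Day 15. Sessions left = 36 − session number of the check day.

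| Hgb check | Session number | Sessions left |
|---|---|---|
| Day 15 | 7 | 29 |
| Day 29 | 13 | 23 |
| Day 43 | 19 | 17 |
| Day 57 | 25 | 11 |
| Day 71 | 31 | 5 |

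These counts assume that ESA treatment is already optimized at the check and that nobody uses discretion. Real exposure would be shorter.

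**Step 5. How often it could arise.** The documents give no Hgb distribution, so the per-subject risk p of meeting the criterion on first-assigned S-15 is an assumption. With 26 / 2 = 13 active subjects, the expected number is 13p and the chance of at least one is 1 − (1 − p)^13.

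| Assumed p | Expected cases | Chance of at least one |
|---|---|---|
| 2% | 0.26 | 23.1% |
| 5% | 0.65 | 48.7% |
| 10% | 1.3 | 74.6% |
| 20% | 2.6 | 94.5% |

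**The case against.** **Discontinuation in Period 1 was clearly planned.** The Section 15.1.2 schedule monitors tolerability at every session under Appendix 17.1, and its footnote 8 allows for subjects already discontinued. SAP 4.7 lists escalation or discontinuation on Day 26 and adds de-escalation only on Day 54. This stands as evidence of intent, as does the revision log. But neither place gives an Hgb criterion; the schedule points back to Appendix 17.1, which has none for this state.

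**Relevant text is not visible.** The log says of Section 2.3.1: "Modified Table 1 to provide more explicit mitigation strategies/preventative measures for IDH and anemia". That table is redacted, and the List of Definitions is also absent from the public copy. Either could hold a rule for this case. This stands, and the conclusion is limited to visible text.

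**A staged response could be deliberate.** On the smallest column, a sponsor might bar escalation, optimize ESA and leave stopping to the investigator. Appendix 17.1 also says *should* where Section 5.4.1 says *will*. The approach would be coherent, but nothing visible states it, and it would not explain why stopping is required on the same column after a step-down.

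**The risk range has no source.** Correct. It shows what would follow from each assumed risk and does not estimate that risk. Entry below 9 g/dL is also excluded.

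**Closing the gap costs subjects in both arms.** At an assumed 10% or 20% in each arm, 26 × 0.10 = 2.6 or 26 × 0.20 = 5.2 subjects would meet the criterion, and controls would be stopped for anemia that no column caused. With 20% drop-out, 26 × 0.80 = 20.8 are evaluable, only 0.8 above target. The cost is real but limited: stops before Week 8 may be replaced (Section 5.4.2), stops after completing Week 8 leave the subject evaluable (Section 10.3), and Section 6.1.5 already requires equal evaluations in both arms.

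**Conclusion.** The concern holds on the operative text. Both Hgb discontinuation provisions require a prior step-down, so a subject below 9 g/dL on first-assigned S-15 triggers a de-escalation that cannot be carried out and then meets no visible mandatory stop. This looks like a drafting gap: the log, the Period 1 schedule and SAP 4.7 all point to discontinuation being intended.

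The consequence is bounded. The subject is on the smallest column and cannot be escalated, clinically significant values are recorded as AEs (Section 7.2.1), and AE-based withdrawal, discretion, medical monitor review and the DSMB all remain. The session counts in the working are upper bounds and the case frequencies rest entirely on assumed risks. The change should be made because a stated safety rule gives different answers for the same subject state. Confidence is moderate, since unseen text could bear on this case.

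**What to change.** In the Hgb criterion of Appendix 17.1 and of Section 5.4.1, replace the step-down condition with wording such as: *while on S-15, whether first assigned or reached by de-escalation*. Make the same replacement in the IDH criterion so that it agrees with Section 7.1.1.2.2; for IDH this is harmonization only. Apply the rule identically in the control arm. If Table 1 in Section 2.3.1 or the List of Definitions already covers this case, align the wording and cross-refer to it.

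The 9 g/dL and IDH thresholds do not change, and the SAP needs no edit. The cost is a short clarifying amendment and possibly a few more early discontinuations across the two arms. Those before Week 8 may be replaced under Section 5.4.2.

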18 REVISION HISTORY

18.1 SUMMARY OF CHANGES

Protocol Version 2.1 dated 14FEB2020

Replaces: Protocol Version 2.0 dated 24JAN2020

The following table describes changes from Version 2.0 (dated 24JAN2020) with justifications provided.

Section(s)	Description	Justification
Throughout	
Protocol version update.
 
Previously read: V2.0_24JAN2020
 
Now reads: V2.1_14FEB2020
	Version control.
5.2	
Previously read: Pregnant or breast-feeding subjects or subjects who are planning to become pregnant. Female subjects must not be pregnant or breastfeeding. Women of childbearing potential (WOCBP) must have a negative serum pregnancy test at Screening, prior to treatment, and at EOS. WOCBP must agree to use highly effective contraception (Clinical Trial Facilitation Group 2014) prior to study entry. A WOCBP is defined as a woman who can become pregnant. Should a woman become pregnant or suspect she is pregnant while she or her partner is participating in the study, she should inform her treating physician immediately
 
Now reads: Pregnant or breast-feeding subjects or subjects who are planning to become pregnant. Female subjects must not be pregnant or breastfeeding. Women of childbearing potential (WOCBP) must have a negative serum/urine pregnancy test at Screening, prior to treatment, and at EOS. WOCBP and men must agree to use highly effective contraception (Clinical Trial Facilitation Group 2014) prior to study entry. A woman is considered of childbearing potential following menarche and until becoming postmenopausal (no menses for at least 2 years without an alternative cause). Should a woman become pregnant or suspect she is pregnant while she or her partner is participating in the study, she should inform her treating physician immediately.
	Reverted to the original language to ensure safety, including the need for male subjects to use highly effective contraception for safety reasons.
15.1.2, 15.1.3, 15.1.4	Updated the Schedule of Events to indicate that local laboratory testing will be performed on Days 15, 43, and 71, as specified in Section 15.2.	For protocol clarity and consistency with the Schedule of Laboratory Tests.

Protocol Version 2.0 dated 24JAN2020
Replaces: Protocol Version 1.2 dated 13NOV2019

The following table describes changes from Version 1.2 (dated 13NOV2019) with justifications provided.

Section(s)	Description	Justification
Throughout	Protocol version update. Previously read: V1.2 13NOV2019 Now reads: V2.0 24JAN2020	Version control.
Throughout	Minor grammar and content updates.	Minor grammar/content updates for clarity/accuracy of content.
Table of Contents	Updated to reflect content changes.	Minor updates required to reflect revised content.
List of Abbreviations	Minor content updates.	Minor updates required to reflect revised content.
List of Definitions	Added List of Definitions.	To clarify important definitions relevant throughout the protocol for evaluation of eligibility and safety monitoring.
Protocol Summary (Précis)	Updated to account for all study visits, including Screening and End of Study.	Revised for clarity and consistency.
Protocol Summary (Précis), 4.1	Added: Subjects who may occasionally require an additional HD session per week would not receive the intervention on that additional day.	Incorporated for clarity to ensure that the column is not used as part of HD more than 3 times per week in subjects who may occasionally require an additional HD session.
Protocol Summary (Endpoints), 4.2.2	Updates to the list of secondary endpoints: Previously read: Feasibility of each column size escalation as measured by subject compliance with study visit schedule/completion, visit procedures, and subject retention. Now reads: 
 • Feasibility of all procedures, including blinding. • Tolerability of each column size escalation as measured by subject compliance with study visit schedule/completion, visit procedures, and subject retention. 	Revised for clarity and inclusion of additional endpoints to enable quantification of the occurrence of IDH and anemia.

	
Added:
 
 • The change in IDH Rate above each subject's Historical IDH Rate for each column size. • The incidence of IDH leading to de-escalation or discontinuation. • The incidence of worsening anemia by column size. • The incidence of anemia leading to de-escalation or discontinuation. 
Previously read: Change from baseline in b2M concentration in post-HD circuit and post-AKST1210 levels by column size and duration of treatment at Week 4, Week 8, and Week 12, and Week 14 at End of Study (EOS) (2 weeks after treatment conclusion).
 
Now reads: Change from baseline in levels of b2M at Weeks 4, 8, 12 and EOS and evaluation of any differences in the magnitude of change based on column size and duration of treatment with a specific column size.
 
Previously read: Change in cognition per the Cogstate test battery (i.e., verbal learning, psychomotor function, visual attention, working memory, executive function, and verbal delayed recall).
 
Now reads: Change in cognitive domains as measured with the Cogstate battery (i.e., verbal learning, psychomotor function, visual attention, working memory, executive function, and verbal delayed recall).
	Revised for clarity and to enable quantification of the occurrence of IDH and anemia.
Protocol Summary (Subject Duration), Schematic of Study Design	Screening period extended from -4 to -2 weeks to -6 to -2 weeks (-42 to -14 days); thus, duration for subjects may be extended an additional 2 weeks (also see changes to Schedule of Study Events [15.1.1] detailed below).	Screening period extended to enhance study feasibility.
2.3.1, Table 1	Modified Table 1 to provide more explicit mitigation strategies/preventative measures for IDH and anemia.	Updated to provide clarity regarding mitigation strategies that serve to minimize the risk of IDH and anemia from occurring in study subjects.
2.3.1	Added: [...] because data on the potential effects of	Updated to provide guidance

	AKST1210 on plasma levels of medications are limited, it is recommended that all IV and oral medications be given after each dialysis session, unless clinically needed before or during dialysis.	as to the timing of IV medications given that data regarding potential clearance of medications is limited.
4.1, Schedule of Events	Extended Screening Visit window from 2 weeks (Day -28 to -14) to 4 weeks (Day -42 to -14).	To enhance feasibility of performing required screening assessments within window.
4.1	Added language to reflect that informed consent may be obtained by a subject's legally authorized representative (LAR) when applicable.	Updated for clarity and consistency with Section 12.
4.1, Schedule of Events	Incorporated language to clarify that the blood sample to assess b2M levels at Screening should be sent to a site's local laboratory.	Updated for clarity and consistency.
4.1, 5.2, Schedule of Events	Incorporated language to clarify that eligibility will be assessed during Run-in.	Updated for clarity and consistency.
4.1	Modified to include a more comprehensive overview of study visit procedures (e.g., targeted physical examinations, monitoring of vital signs).	Updated for clarity and consistency with Section 7 and the Schedule of Events.
5.1	
Previously read: 5. Medical records indicating occurrence of < 5 intradialytic hypotensive events related to HD in 8 weeks prior to randomization.
 
This has been revised to be an exclusion criterion (see Section 5.2, new #7, bullet 1) and Now reads: Subjects with medical records indicating the occurrence of ≥ 5 events of IDH during a recent, consecutive 8-week interval prior to randomization.
 
Modified the window in which subjects should be on a stable regimen of either medications for cognition and/or antidepressants to be 8 weeks prior to Screening.
	
Updated for clarity and to enhance protocol feasibility in obtaining sufficient medical records to assess a subject's Historical IDH Rate.
 
Updated for clarity and to help ensure consistency in results obtained from the scales conducted during Screening.

5.2	
Updated exclusion criterion #2 as follows:
 
Previously read: Subjects who are not able to tolerate extended duration of > 4 hours at a maximum flow rate of 250 mL/min.
 
Now reads: During Run-in, subjects who are not able to comply with or tolerate extended HD duration of approximately 4 hours at a maximum flow rate of 250 mL/min as assessed by the investigator.
 
Added exclusion criterion #3 as follows:
 
Subjects who experience 3 or more IDH events
	Clarification of evaluation period for tolerability of flow rate.
		Incorporated to clarify

	
during the Run-in period.
 
[REDACTED]
 
[REDACTED]
 
[REDACTED]
 
[REDACTED]
 
Updated exclusion criterion #5 (previously #4) as follows:
 
Previously read: Subjects for whom extracorporeal circulation therapy is contraindicated, such as those with severe cardiac insufficiency, acute myocardial infarction, severe cardiac arrhythmia, acute seizure disorder, severe uncontrolled hypertension, or hypotension requiring or expected to require extensive fluid management.
 
Now reads: Subjects for whom extracorporeal circulation therapy is contraindicated, such as those with severe cardiac insufficiency, acute myocardial infarction, severe cardiac arrhythmia, acute seizure disorder, or severe uncontrolled hypertension.
 
Updated exclusion criterion #7 (previously #6) as follows:
 
Previously read: Subjects who are at a high risk of hypotension from their HD history based on investigator assessment.
 
Now reads: Subjects who are at a higher risk of IDH including:
 
• Subjects with medical records indicating the occurrence of ≥ 5 events of IDH during a recent, consecutive 8-week interval prior to the Run-in period;• Subjects requiring or expected to require	
evaluation of IDH events during Run-in and define parameters for exclusion
 
[REDACTED]
 
Moved content regarding hypotension and more clearly defined this in exclusion criterion #7.
 
Incorporated additional exclusion criteria to clarify exclusion criteria for subjects at a higher risk of IDH; all exclusion criteria pertaining to hypotension have been grouped together for clarity.

--	--	--

	
extensive fluid management;
 
 • Presence of pre-dialysis hypotension, defined as a systolic blood pressure (SBP) < 90 mm Hg and/or a diastolic blood pressure (DBP) < 50 mm Hg, before any of the last 3 dialysis sessions prior to screening; • A diagnosis of interdialytic hypotension; • A diagnosis of IDH; and/or • A diagnosis of autonomic dysfunction. 
Updated exclusion criterion #8 (previously #7) as follows:
 
Previously read: Pregnant or breast-feeding subjects or subjects who are planning to become pregnant. Female subjects must not be pregnant or breastfeeding. Women of childbearing potential (WOCBP) must have a negative serum/urine pregnancy test at Screening, prior to treatment, and at EOS. WOCBP and men must agree to use highly effective contraception (Clinical Trial Facilitation Group 2014) prior to study entry. A woman is considered of childbearing potential following menarche and until becoming postmenopausal (no menses for at least 2 years without an alternative cause). Should a woman become pregnant or suspect she is pregnant while she or her partner is participating in the study, she should inform her treating physician immediately.
 
Now reads: Pregnant or breast-feeding subjects or subjects who are planning to become pregnant. Female subjects must not be pregnant or breastfeeding. Women of childbearing potential (WOCBP) must have a negative serum pregnancy test at Screening, prior to treatment, and at EOS. WOCBP must agree to use highly effective contraception (Clinical Trial Facilitation Group 2014) prior to study entry. A WOCBP is defined as a woman who can become pregnant. Should a woman become pregnant or suspect she is pregnant while she or her partner is participating in the study, she should inform her treating physician immediately.
 
Added exclusion criterion #12 as follows: Subjects on anti-seizure medications for a seizure disorder.
	
Revised to clarify that women who have undergone sterilization are not considered WOCBP; removed urine pregnancy test as only a serum pregnancy test will be used; eliminated the need for men to use highly effective contraception based on safety information from previous trials.

--	---	---

	
Added exclusion criterion #14 as follows: Subjects with a hemoglobin level < 9 g/dL.
 
Updated exclusion criterion #15 (previously #12) as follows: Previously read: Concurrent or recent participation in another investigational clinical trial.
 
 Prior clinical trial subjects must have discontinued investigational agents at least 30 days prior to Screening for small molecules, and 1 year prior to Screening for vaccine or immunotherapy agents. 
Now reads: Concurrent or recent participation in another investigational clinical trial. Prior clinical trial subjects must have discontinued investigational agents at least 30 days prior to Screening.
 
Updated exclusion criterion #16 (previously #13) as follows: Previously read: History of severe depression/suicidality requiring hospitalization.
 
Now reads: History of severe depression/suicidality requiring hospitalization in the last 6 months.
	
Incorporated to exclude subjects with anemia.
 
Clarification of timing of use for investigational agents prior to Screening.
 
Clarification of timing of hospitalization for severe depression/suicidality.

5.3, 5.4.2	Content revised to indicate that subjects who discontinue or are unblinded prior to Week 8 may be replaced (previously indicated prior to Week 5).	Revised to provide clarity regarding timing for replacement of subjects.
5.4.1	
Added:
 
 A subject will be discontinued if the number of IDH events during a treatment period exceeds a predetermined threshold above the subject's Historical IDH Rate after de-escalation to the lowest column size (see Appendix 17.1). A subject will be discontinued if hemoglobin levels remain < 9 g/dL despite optimized iron and ESA treatment and after de-escalation to the lowest column size (see Appendix 17.1). 	Clarification to align with revised Definitions, study procedures, and Appendix 17.1.
6.1.2.1	Clarified that the control will consist of a covered surrogate object of similar size/shape as the AKST1210 column and incorporated a reference to the Device Procedures Manual.	Revised for clarity and consistency.
6.1.5	Added: Careful attention should be given to ensure that all subjects, regardless of treatment assignment, undergo the same evaluations for escalation, de-escalation, and discontinuation.	Added for clarity and to ensure adequacy of blinding procedures.
6.1.6	Removed Section 6.1.6 Route of Administration	Route of administration is not

		applicable, and information regarding how the device is connected to the circuit is described elsewhere in the protocol (6.1.4) and Device Procedures Manual.
7.1.1.1, Schedule of Study Events (15.1.1-15.1.5)	Updated to account for all procedures performed at Screening and during Run-in. Added: The Screening Visit may be split to allow for sufficient time to complete all required procedures.	To provide clarity and consistency. A split visit at Screening is intended to aid feasibility.
7.1.1.1.5, 7.1.1.9, 7.1.1.2.5, 7.2.1, 7.2.3, Schedule of Study Events (15.1.1-15.1.5)	Modified to more clearly specify laboratory tests that should be conducted at Screening and Run-in and which laboratory tests should be performed locally versus those required to be stored and shipped to a repository. Samples for screening labs should be collected either on a non-dialysis day or prior to HD. In addition, urine testing will be eliminated.	Updated to provide enhanced clarity; urine testing removed.
7.1.1.1.6	Added a reference to Table 1 in Section 2.3.1 to highlight proposed mitigations for known safety risks, such as IDH and anemia.	Updated to provide cross-reference to additional assessments for enhanced safety.
7.1.1.1.6.1	Created a subsection to 7.1.1.1.6 specific to heparinization procedures and restructured the content to more clearly specify the guidance for de-escalation of heparinization.	Updated for clarity.
7.1.1.1.9	Content revised to indicate that detailed procedures for b2M collection will be included in the AKST1210 b2M and Proteomics Lab Manual.	Updated for clarification of location of details for procedures related to collection of b2M and proteomics.
7.1.1.2	Updated to provide a more comprehensive list of procedures performed to assess safety (e.g., targeted physical exams, weight measurements).	Updated for clarity.
7.1.1.2.2	Added an assessment for cognitive dysfunction (confusion, alteration of consciousness) in the context of IDH. Added that BP can be obtained in a seated or reclined position. Added procedures related to evaluation of IDH.	Updated to enable prompt identification and intervention in the event of decreased cerebral blood flow in the context of IDH and/or hypovolemia Clarification for positioning options for BP. Clarification of monitoring for IDH.
7.1.1.2.4	Updated to describe a “targeted” physical examination versus a (complete) physical examination as described in Section 7.1.1.1.3	Revised to differentiate between a “targeted” physical examination and (complete)

		physical examination.
7.3.4	Updates/removal of duplicative content related to withdrawal and evaluation.	Clarification of content.
7.5	Updated the list of prohibited concomitant medications, treatments, and procedures.	Revised for clarity and consistency with the Inclusion/Exclusion Criteria.
8	
Previously read: Assessment of safety will be conducted by blinded study personnel except in extraordinary circumstances where knowledge of whether AKST1210 was received by a subject is essential.
 
Now reads: Assessment of safety will be conducted by blinded study personnel who are medically qualified by training and experience (e.g., study investigators) except in extraordinary circumstances where knowledge of whether AKST1210 was received by a subject is essential.
	Added to clarify assessment of safety.
8.5, 8.6	Modified to indicate that safety oversight will be under the direction of a Data and Safety Monitoring Board (DSMB).	Added to clarify safety oversight.
10.3, 10.5	Defined the evaluable dataset as all subjects who complete through Week 8.	The definition of Evaluable subjects for analysis had not been included previously. Further details on the statistical populations will be included in the Statistical Analysis Plan.
13.3	Updated the definitions of Major and Minor Protocol Deviations and included examples of each for clarity.	To align with the definitions in Alkahest's SOP-CL-007 on Protocol Deviations Oversight and Reporting.
Schedule of Study Events (15.1.1 – 15.1.5), Schedule of Laboratory Tests	Revisions to study events/timing and laboratory testing. Key changes relate to extension of Screening period from -4 to -2 weeks to -6 to -2 weeks (now -42 to -14 days [previously -28 to -14 days]), removal of laboratory samples that are not relevant to the subject population, and additional testing of Hgb to support monitoring for anemia.	Revised to align with changes described in the protocol, specifically Section 7.
